5.3 Informed Consent and Randomization

5.3.1 Telephone screen, consent, and baseline assessment:

For those potential participants who do not return an opt-out postcard within 2 weeks (as well as those who return the opt/in card and those that opted in via Qualtrics), a research coordinator may telephone to:

- Describe study and answer questions.
- Assess eligibility, including potential exclusions for safety. (Section 5.4)
- Obtain consent under a waiver of documentation of written informed consent.
- Administer baseline surveys; or participant may complete online versions or paper copies and return via postage-paid mail.

5.3.2 Medical clearance:

For individuals who consent at the telephone screen and have fulfilled safety requirements, study staff will send a secure email to the patient's primary care provider to inform them of their patient's participation and to alert us if there is any reason that their patient should not participate. If the primary care provider does not respond after four days, we will send a second email. If no response to the second email, we will send a third email informing the PCP that we will enroll the individual in three business days unless they contact us otherwise. We will inform interested participants if their provider responded that this intervention is not appropriate.

As outlined in section 5.5.6, a subset of POWER subjects will be selected to have a single-night diagnostic home sleep study at 1 year. Among those selected for this sleep study, study staff will send a secure email to the patient's primary care provider and, if available, their sleep specialist. This email serves to inform their providers of their patient's participation in a single-night sleep study, asks if they have any concerns about their patients' participation in this diagnostic sleep study, and states that we will proceed with the sleep study unless the specialist contacts us within five business days. As diagnostic sleep studies, proposed in this trial, are often used as part of usual care to diagnose OSA and observe changes in patients' OSA severity over time, we do not expect that many providers will object to participation.

5.3.3 Randomization:

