5.4 Inclusion/Exclusion Criteria

Veteran Participant eligibility criteria: As we describe in more detail below, we will utilize the CDW to identify Veterans with recent sleep study and diagnosis of OSA with measured body mass index (BMI) between 30.0-44.9 kg/m² recorded in the past three months. Including patients with recent sleep study will increase likelihood of accurately identifying participants with OSA,⁶⁰ and will allow recruitment after initial diagnosis or reassessment when patients may be more amenable to behavior change interventions.⁶¹

To minimize spurious inclusion, we will ensure an additional BMI within the past 12 months of index weight that meets criteria set by a standard algorithm to remove implausible and erroneous BMI values.^{29,62,63} Specifically, we use the criteria used previously for the D-ELITE trial^{62,63} to exclude any index weight indicating excessive weight change prior to the index date: >40-pound change in any 30-day period in past year, or more than two pounds change per week over periods greater than 30 days. To exclude plausible but likely invalid index weights, we excluded weights if 1) the standard deviation of the difference between index and any past-year weight is greater than 5% of the average weight, 2) if the weight change is greater than ± 100 pounds in a year, or 3) if the BMI change is greater than ± 15 kg/m². We also exclude weights greater than 500 pounds or less than 90, height < 49 or > 84 in., and BMI greater than 65 or less than 15 kg/m² (calculated using the most recent height measurement between 49 and 84 in.). We apply the same algorithms for flagging potentially implausible and erroneous weights for outcome measurement (Section 5.5.2).

We will also confirm OSA by reviewing sleep studies, among those who have not opted out, prior to enrollment. We will calculate index and previous BMI using most recent height and weight. Exclusion criteria are chosen to ensure participant safety, while maximizing internal validity, and minimizing error caused by missing and misclassified data (Table 4).

Table 4: Inclusion and Exclusion Criteria

Inclusion

- Diagnosis of OSA on sleep study (sleep provider confirmed)
- Clinical BMI between ≥ 30 , $< 45 \text{ kg/m}^2$, and at least one additional plausible BMI in last 12 months
- Access to television and DVD player, computer with USB drive, or internet
- Able to participate fully in all study protocol/procedures including informed consent

Exclusion

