5.5.5. Physiologic OSA Severity: Including AHI as a secondary outcome measure in this pragmatic trial will be needed to contextualize our intervention's impact for the sleep clinicians and policymakers who continue to rely on AHI as an "objective" marker. We will conduct sleep studies among a subset of participants to compare the impact of the intervention on AHI and estimate the proportion of patients with resolution of detectable OSA. Testing all 696 patients is not feasible in our budget. Therefore, we will select up to n=125 participants in each treatment arm to undergo home sleep apnea testing (HSAT) using level 3 home sleep apnea tests at the

12-month follow up. We will contract with a company, Sleep Care, Inc, to perform these home sleep apnea tests.

We will quantify OSA severity with the apnea hypopnea index, with hypopneas defined using both the 4% and 3% desaturation rules, AHI4% and AHI3%. Of the two, we will prioritize the AHI4% as our measure of highest interest. Prior to distributing tests, we will conduct chart reviews to assess for safety issues that might make pausing treatment for one night unsafe (e.g., severe sleep-related hypoventilation). Following chart review, we will contact patients who expressed an interest at recruitment and are currently using reversible treatments (e.g., CPAP) and ask if they are still interested and able to pause treatment for one night. We will verify safety by asking about daytime sleepiness and any recent heart-related hospitalizations or issues.²²² We will also contact patients' providers to ensure that OSA treatment can be held for one night to assess untreated sleep. Following the call to the participant and contacting the provider, we will email or fax the patient's contact information to Sleep Care, Inc to arrange delivery and instructions for the HSAT.

If results of the home sleep test reveal a previously unknown concerning result such as severe sleep related hypoxemia (low levels of oxygen), sustained bradycardia (low heart rate), sustained tachycardia (high heart rate), or serious arrhythmia such as atrial fibrillation or ventricular tachycardia, study staff will contact the participant and discuss the findings. Study staff will inform the participant that they will also contact the participant's VA primary care provider and/or sleep specialist and make them aware of the finding.

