We fully acknowledge that ongoing COVID-19 related changes in clinic utilization may alter the feasibility of the clinic-based approach. As a contingency, we also will request that participants weigh themselves with study-provided scales and report measured

weights shortly after randomization as well at 3-, 12-, and 21-month follow-up. Under a contingency approach that we will explore in secondary/sensitivity analyses, if a subject is missing a clinical weight, we will substitute self-collected weights in the analysis. We will provide written and verbal instructions to approximate clinic-based weights (e.g., clothed, but no shoes or jackets). Should we experience widespread clinic closures, limiting assessments of clinic weights, we may consider substituting clinic-based weights with self-weights in our primary analysis. We would make such a decision prior to analyzing primary outcomes.

Secondary outcomes: We will collect secondary outcomes including cardiovascular risk scores (non-laboratory Framingham), blood pressure, treatment adherence, and sleep symptoms (PROMIS measures) using a combination of surveys and CDW data. We will also mail home sleep apnea tests in a subset of patients at 12 month follow up only to understand impacts on physiologic severity of OSA.

All Veteran subjects will be remunerated \$25 upon completion of the 12-month surveys, \$25 for participation in the home sleep apnea test and \$25 upon completion of any outcome surveys at the close of the study.

4. Method of Randomization:

The unit of randomization will be the patient, performed at a ratio of 1:1 within strata using the permuted-block method within block sizes of 4. Given three stratifying variables of BMI category (30-34.9 vs. 35-44.9 kg/m²), physiologic OSA severity (moderate to severe as defined by interpreting physician or apnea hypopnea index ≥ 15 events/hour vs. otherwise), and sleep related impairment (PROMIS Sleep Impairment T-score ≥ 60 vs. T-score < 60) there will be 8 strata. Research assistants recruiting patients will remain blinded to randomization assignment sequences. Following baseline assessment, we will assign patients from each stratum to intervention or control using predetermined randomly generated sequences. Patients will be informed of their randomization assignment via mail. This will ensure a balanced number of patients in each stratum in the intervention and control groups. Stratification will help prevent covariate imbalance between groups.

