 - While our proposed sample size has not changed, we now present power analyses for between group differences for change in weight focused on a difference in the range of 3% weight loss, which is more widely accepted as clinically meaningful ([name] et. al., JAMA. 2023. PMID: 36511927)
 - The target sample size of 696 is still required to identify a clinically meaningful difference in our co-primary endpoint of functional outcomes of sleep questionnaire.

Section 3. Description of how data will be collected:

- Revised to state that the co-primary outcome of weight will only include clinically measured weights identified from CDW, as contingencies around self-weight are not currently needed given the current state of clinic operations.
- Also clarified that self-weights are not measured at baseline, but rather shortly following randomization, when intervention scales are sent.
- Updated description of home sleep apnea testing to confirm that these tests will only be collected at 12 months, not at baseline as we originally planned (see changes to secondary outcome hypothesis 2b to accommodate).
- Clarified timing of participant reimbursement.

- Section 4. Method of Randomization:
 - Removed gender as a stratification variable, although we will retain as a subgroup analysis (see edits to section 7 and 9 as well).
 - Prior to the start of randomization in April 2023, our biostatistician had concerns that a large number of strata could lead to imbalance in randomization. Our biostatistician was particularly concerned about gender as a stratification variable given the relatively small number of women Veterans. In order to avoid imbalance, our biostatistician recommended that we limit strata to the three variables for which we anticipated a

relatively equal distribution between categories. We implemented this change prior to the start of randomization.

Section 6. Missing Data

- Explicitly stated that we will test our hypotheses using a complete case analysis.

Section 9. Definitions of the analytic cohorts:

- Revised language around hypotheses to specifically denote primary and secondary hypotheses.
- Added formal hypothesis (H2b) for comparing secondary outcomes between groups at a single time point. This is the case for apnea hypopnea index as research HSATs will only be collected at 12 months.

Section 10. Adverse and Serious Adverse Event Monitoring

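### A single 12-month home sleep test with no matching baseline test cannot give a proportion with resolved OSA; it can give a proportion with no detectable OSA, compared between arms

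*Protocol*

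**What the plan says.** Protocol 5.5.5 gives the sleep studies two purposes: to compare the intervention's effect on AHI, and to "estimate the proportion of patients with resolution of detectable OSA". For this, "we will select up to n=125 participants in each treatment arm".

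**Follow-up test.** It is a level 3 home test from one contractor (Protocol 5.5.5). Protocol 5.3.2 makes it one night: "a subset of POWER subjects will be selected to have a single-night diagnostic home sleep study at 1 year". SAP Section 3 limits it to one occasion: "We will also mail home sleep apnea tests in a subset of patients at 12 month follow up only". Hypopneas are scored by both the 4% and the 3% rule, and AHI4% has priority.

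**Baseline.** The SAP's edit log, in line with its current text, confirms that "these tests will only be collected at 12 months, not at baseline as we originally planned". The only baseline value is a clinical AHI from chart review (Protocol Table 5). It comes from a study under any of five procedure codes (Protocol 5.2.3). Entry requires a sleep-provider-confirmed diagnosis, with no AHI threshold or hypopnea rule (Protocol 5.4, Table 4).

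**Analysis.** H2b compares 12-month values between arms (Protocol 3.0 and 5.6.2; SAP Section 9). Outcomes collected only at follow-up use the trial model without baseline values. The SAP does not mention the resolution proportion.

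**The concern.** Resolution means present before and absent now. To observe it, a patient has to be measured on both occasions in a comparable way. Here patients are selected because one reading was positive. They are then read once more, possibly by a different type of test and under a different scoring rule. Some whose disease has not changed will fall below whatever cut-off is chosen.

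Protocol 5.5.5 says AHI is included for sleep clinicians and policymakers. A statement that a given percentage of the intervention arm had resolution would be easy for that audience to quote. It would credit the programme with negative tests that also occur under usual care.

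**Working it through.** The documents give no expected rate, cut-off or sample size for this proportion, so there is no figure of the plan to reproduce. The check has three steps.

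**1. Are the two readings comparable?**

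| Feature | At entry | At 12 months |
|---|---|---|
| Test | Any of five procedure codes | Level 3 home test, one contractor |
| Scoring | Not stated | AHI4% first, AHI3% also |
| Threshold | Provider's diagnosis | Not stated |
| Role | Selects patients as positive | Classifies them once |

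The only AHI cut-off in either document is 15 events/hour. It defines a stratum (Protocol 5.3.4; SAP Section 4), not resolution.

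**2. How many unchanged patients could read as resolved?** All inputs here are assumptions:
- Entry reading of at least 5, and resolved means a second reading below 5.
- Readings log-normal with median 15 or 20 and geometric SD (g) 2.0 or 2.5.
- Test-retest ICC on the log scale 0.7 or 0.9.
- No true change. The second test reads k times the first method, with k = 1, 0.75 or 1.25.

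Let a = (ln 5 - ln median)/ln g and c = (ln(5/k) - ln median)/ln g. With Φ the standard normal and Φ₂ the bivariate normal distribution function with correlation ICC,

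share = [Φ(c) - Φ₂(a, c; ICC)] / [1 - Φ(a)].

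Example with median 15, g = 2.5, ICC 0.7 and k = 1: a = c = (1.609 - 2.708)/0.916 = -1.199. Then Φ(a) = 0.1153 and Φ₂ = 0.0560, so the share is (0.1153 - 0.0560)/0.8847 = 0.067.

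| Median | g | ICC | k = 1 | k = 0.75 | k = 1.25 |
|---|---|---|---|---|---|
| 15 | 2.0 | 0.7 | 3.57% | 9.12% | 1.48% |
| 15 | 2.0 | 0.9 | 2.12% | 7.53% | 0.55% |
| 15 | 2.5 | 0.7 | 6.70% | 12.84% | 3.70% |
| 15 | 2.5 | 0.9 | 3.91% | 9.90% | 1.54% |
| 20 | 2.0 | 0.7 | 1.57% | 4.53% | 0.60% |
| 20 | 2.0 | 0.9 | 0.96% | 3.79% | 0.23% |
| 20 | 2.5 | 0.7 | 4.05% | 8.27% | 2.13% |
| 20 | 2.5 | 0.9 | 2.40% | 6.43% | 0.90% |

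The ranges are 1.0-6.7% for an identical test, 3.8-12.8% if the home test reads 25% lower, and 0.2-3.7% if it reads 25% higher. Multiplied by 125, these are about 1 to 8, 5 to 16, and 0 to 5 patients per arm.

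A separate simulation used other assumptions: median 12, 20 or 30; between-patient log-SD 0.8; single-night log-SD 0 to 0.5; follow-up reading 1.0, 0.85 or 0.7 times the first method. The share was zero only with neither night-to-night error nor a method shift. Otherwise it ran from 0.5% to 19.4%. Most of it came from patients with an entry reading of 5 to under 15 (2.7% to 32.6% of them). Among those at 15 or above it was 0% to 5.8%.

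**3. Does this carry over to the between-arm comparison?** Both arms have the same 12-month test. With a common spurious rate of 5%, 10% or 20% and 125 per arm, the simulated mean difference was zero and the two-sided type I error at nominal 0.05 was 0.046 to 0.051. Misclassification of this kind does not by itself bias the contrast, provided the tested patients are comparable across arms.

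**The case against.** The strongest reply is that the plan already makes the right comparison. H2b is a between-arm test, the follow-up-only model omits baseline values, and it includes the stratification variables, one of which is baseline OSA severity. Up to 125 patients are tested in each arm, so per-arm proportions and their contrast are the natural output. The measure is secondary, has no hypothesis of its own, and covers at most 250 of 696 patients (36%).

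Most of this stands. A reader might infer that the sponsor plans a single-arm headline figure, or that H2b is biased. The documents support neither: no pre-post or single-arm claim is described, and H2b needs no baseline test. A reader might also infer that any reported proportion would overstate improvement by a known amount. The documents do not give the size, or the direction of any shift between the clinical and the home test. If the home test reads higher, fewer unchanged patients are misclassified, and some true improvement could be missed.

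The reply does not cover the proportion itself. It is named as a resolution rate, it has no cut-off, it is absent from the SAP, and nothing restricts it to a between-arm contrast.

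It would also go too far to say that the between-arm difference is interpretable without conditions. The subset is settled after randomisation. It depends on interest expressed at recruitment, chart review and provider contact. Patients on reversible treatment are also asked whether they remain interested and able to pause it for a night. The contrast is unbiased only if this selection does not differ by arm.

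**Conclusion.** The point holds as a matter of definition and reporting. The design can estimate the proportion with no detectable OSA on a home test at 12 months. It cannot estimate the proportion whose OSA resolved.

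The number of unchanged patients who would be labelled resolved is unknown. The illustrative figures (about 1-7%, 4-13% and 0.2-4% for a home test reading the same, 25% lower and 25% higher) depend on the assumed cut-off of 5, the entry condition, the AHI distribution and the ICC, none of which is in the documents. Because entry has no AHI threshold, some patients may already be below an AHI4% cut-off when they enrol. The calculation leaves them out.

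Neither co-primary outcome nor the mean AHI comparison in H2b is affected. The priority is low, but the repair is cheap. The same gap applies to the plan in 5.5.5 to assess changes in other markers of respiration and oxygenation.

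**What to change.** In Protocol 5.5.5, and in a matching line in the SAP:

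1. Rename the measure *no detectable OSA on the 12-month home test*.
2. Have the sponsor set the AHI4% cut-off before the home-test results are analysed. The choice is the sponsor's. If results have already been examined, say so when reporting.
3. Report the proportion by arm, with the between-arm difference and 95% CI, adjusted for the stratification variables.
4. State that within-arm proportions will not be presented as resolution.
5. State that the contrast assumes selection into the tested subset does not differ by arm. Report the numbers invited and tested, and their baseline characteristics, by arm.

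This takes a few sentences and no new data collection. The cost is that the sponsor gives up a within-arm resolution figure.
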